2.2 Secondary objectives

The secondary objectives of this study are to:

- Investigate the safety and tolerability of single doses of AZD6244 in healthy male volunteers
- Estimate within-volunteer variability in the PK of AZD6244
- Establish the relative bioavailability of AZD6244 after oral administration of single doses of blue capsules (planned Phase III) with respect to an oral solution formulation
- Characterize the PK of *N*-desmethyl AZD6244 after oral administration of single doses of AZD6244 white (current Phase II) and blue (planned Phase III) capsules

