5.2 Subject enrollment, randomization, and initiation of investigational product

The Investigator (or designee) will:

1. Obtain signed informed consent from the potential volunteer before any study-specific procedures are performed
2. Assign potential volunteers a unique enrollment number, beginning with 'E0001001'
3. Determine volunteer eligibility. See Sections 4.1 and 4.2.
4. Assign eligible volunteers a unique randomization code (volunteer number), beginning with '1001'

If a volunteer withdraws from participation in the study, then his randomization code cannot be reused. If the volunteer is replaced, the replacement volunteer will be assigned the next available volunteer number from the randomization.

Procedures for randomization

Up to 30 healthy male volunteers (aged 18 to 55 years) will be enrolled. For Dosing Period 1 only, the first two volunteers enrolled will be dosed at least 2 days before the remainder of the volunteers. A randomization scheme will be produced Global Phase I using the global randomization system. Volunteers will be randomized to 1 of the 6 sequences as shown in Table 5.

Table 5 Randomization sequences

Sequence	Dosing Period 1	Dosing Period 2	Dosing Period 3	Dosing Period 4
1	A	B	C	B
2	A	C	B	B
3	B	A	C	B
4	B	C	A	B
5	C	A	B	B
6	C	B	A	B

Treatment A will consist of three 25-mg AZD6244 (current Phase II) capsules.

Treatment B will consist of three 25-mg AZD6244 blue (planned Phase III) capsules.

Treatment C will consist of 35 mg AZD6244 solution.

5.3 Procedures for handling subjects incorrectly enrolled, randomized, or initiated on investigational product

Volunteers who fail to meet the inclusion/exclusion criteria should not, under any circumstances, be enrolled or receive study medication. There can be no exceptions to this rule.

Where volunteers who do not meet the selection criteria are incorrectly started on treatment, or where volunteers subsequently fail to meet the study criteria post-initiation, a discussion should occur between the AstraZeneca Clinical Pharmacology Alliance (CPA) Physician and the Investigator regarding whether to continue or discontinue the volunteer's treatment. The AstraZeneca CPA Physician is to ensure all such decisions are appropriately documented. In situations where an agreement cannot be reached, further administration of the IP should be stopped.

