Primary PK parameters are AUC and C_{\max} of AZD6244. If AUC is not reportable in more than 60% of the 30 enrolled volunteers (ie, 18 reportable AUCs) then $AUC_{(0-t)}$ will be used in the inferential analysis.

Utilizing data from the first three treatment periods only, the relative bioavailability between treatments will be assessed between test (Treatment B) and reference (Treatments A) treatments. Analyses will be performed using a linear mixed-effect analysis of variance model using the logarithm of AUC and C_{\max} as the response variables, sequence, period, and treatment as fixed effects, and volunteer nested within sequence as a random effect. Transformed back from the logarithmic scale, geometric least-squares means together with confidence intervals (CIs) (2-sided 95%) for AUC and C_{\max} will be estimated and presented.

Also, ratios of geometric least squares means together with CI (2-sided 90%) will be estimated and presented.

Using a similar model as above, comparisons will be made for dose-normalized AUC and C_{\max} between test (Treatment B) and reference (Treatments C) treatment. AUC and C_{\max} will be dose-normalized prior to the ln-transformation.

Comparisons include:

- Treatment B versus A
- Treatment B versus C

Using treatment B data only, estimates of between and within-volunteer variability's will be obtained by employing a linear mixed-effect analysis of variance model using the logarithm of AUC and C_{\max} as the response variables and treatment as fixed effect. Volunteer nested within sequence will be a random effect. Treatment will be re-coded as B1 and B2, where B1 will correspond to Treatment B given in the first 3 periods and B2 will correspond to Treatment B given in Period 4. Estimates for the between and within-volunteer variability's will be present together with the associated 90% CIs.

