12.3 Determination of sample size

AUC₍₀₋₁₂₎ and C_{max} data from Study D1532C00005 (Part A, Day 1 single dose and Day 8 steady state) have been used to provide estimates of within-volunteer variability. Based on the estimate of within-volunteer variability of 0.04, 24 evaluable volunteers (4 per sequence) will provide 95% power to show that the 90% CI for the ratio of the population geometric means, based on log-transformed data, is contained in the limits of 80.00% to 125.00% for AUC. Based on the estimate of within-volunteer variability of 0.13 and a sample size of 24 volunteers, the upper limit of the 80% CI of an observed increase in C_{max} of 25% would be 1.43, which is considered clinically acceptable. In order to ensure that 24 evaluable volunteers complete the study, 30 volunteers (5/sequence) will be recruited.

Revised Clinical Study Protocol
Drug Substance AZD6244
Study Code D1532C00066
Edition Number 1
Date

The number of volunteers who will agree to participate in the genetic research is unknown. It is therefore not possible to establish whether sufficient data will be collected to allow a formal statistical evaluation or whether only descriptive statistics will be generated.

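### The Treatment B variability model omits period, so any differences among Periods 1 to 3 are counted as within-volunteer variance

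*Protocol*

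**What the plan says.** Section 2.2 makes this a secondary objective: "Estimate within-volunteer variability in the PK of AZD6244". Section 12.2.2 fixes the model: "Using treatment B data only, estimates of between and within-volunteer variability's will be obtained by employing a linear mixed-effect analysis of variance model", with log AUC and log Cmax "as the response variables and treatment as fixed effect. Volunteer nested within sequence will be a random effect". Treatment is re-coded, "where B1 will correspond to Treatment B given in the first 3 periods and B2 will correspond to Treatment B given in Period 4". The variance estimates are to be reported with 90% CIs. Period does not appear in this model.

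The B versus A model in the same section does include period. Its terms are "sequence, period, and treatment as fixed effects, and volunteer nested within sequence as a random effect".

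Section 5.2 states: "Volunteers will be randomized to 1 of the 6 sequences as shown in Table 5". Reading that table for Treatment B:

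| Sequences | Period of B1 | Period of B2 |
|---|---|---|
| 3, 4 | 1 | 4 |
| 1, 6 | 2 | 4 |
| 2, 5 | 3 | 4 |

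**The concern.** The residual variance is itself the result of this analysis, so a systematic effect that the model fails to remove goes straight into the answer. B1 is not one occasion but three, spread evenly over Periods 1, 2 and 3 by sequence. A two-level B1/B2 factor can take out only the contrast between Period 4 and the average of the first three periods.

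The volunteer random effect cannot absorb the rest, because a period difference acts between a volunteer's own two B observations. If Periods 1 to 3 differ, the reported within-volunteer variance is too high on average and its 90% CI covers less often than stated. The protocol writes this model out in full, so the omission is not a detail left for the SAP.

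**Working it through.** **Inputs**

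- Within-volunteer variability: 0.04 for AUC and 0.13 for Cmax (section 12.3).
- 24 evaluable volunteers, 4 per sequence (section 12.3). Two sequences share each B1 period, so 8 volunteers take B1 in each of Periods 1, 2 and 3 (Table 5).
- Period effects: not given anywhere. All values below are assumptions.

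**Step 1. Reproduce the plan's figures, to fix the scale of 0.04 and 0.13.** Section 12.3 says: "Based on the estimate of within-volunteer variability of 0.04, 24 evaluable volunteers (4 per sequence) will provide 95% power". Read as a log-scale variance, 0.04 gives a standard error of sqrt(2 × 0.04/24) = 0.0577. The power of two one-sided tests within 80.00% to 125.00% is then 96.4% (22 df) or 96.9% (44 df) at a true ratio of 1.00, and 95.4% or 96.0% at 1.02. The true ratio is not stated. For Cmax, 1.25 × exp(1.2816 × sqrt(2 × 0.13/24)) = 1.428, against the stated 1.43. Both figures reproduce, so 0.04 and 0.13 are log-scale variances.

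**Step 2. Expected value of the planned estimate.** Let d = B1 − B2 on the log scale for one volunteer. With two observations per volunteer, the model's within-volunteer variance is the sample variance of d divided by 2, with 23 df. If π_i is the effect of the period in which volunteer i takes B1, then

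E(estimate) = σ_w² + ½ × Σ(π_i − mean π)²/(n − 1).

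The Period 4 effect is common to all volunteers and cancels.

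**Step 3. Equal log steps s across Periods 1, 2 and 3.** The deviations are −s, 0 and +s with 8 volunteers each, so Σ(π_i − mean π)² = 16s². The added variance is ½ × 16s²/23 = 0.348s².

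For coverage, 23 × estimate/σ_w² follows a non-central chi-square distribution with 23 df and non-centrality 16s²/(2σ_w²). The interval covers when this quantity lies between 13.09 and 35.17, the 5% and 95% points of the central chi-square.

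| Log step s | Period 3 vs Period 1, exp(2s) | Added variance | AUC (0.04) | Cmax (0.13) | AUC 90% CI coverage |
|---|---|---|---|---|---|
| 0 | 1.00 | 0 | 0.0400 (0%) | 0.1300 (0%) | 90% |
| 0.05 | 1.11 | 0.0009 | 0.0409 (+2%) | 0.1309 (+1%) | 90% |
| 0.10 | 1.22 | 0.0035 | 0.0435 (+9%) | 0.1335 (+3%) | 88% |
| 0.15 | 1.35 | 0.0078 | 0.0478 (+20%) | 0.1378 (+6%) | 82% |
| 0.20 | 1.49 | 0.0139 | 0.0539 (+35%) | 0.1439 (+11%) | 70% |

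Two other patterns for AUC: if only Period 1 is 10% higher, the estimate is 0.0411 (+2.6%). If only Period 4 differs, it stays at 0.040.

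**Step 4. Which term cures it.** REML fits to 150 simulated trials, with true variance 0.04 and Periods 1 to 4 at 0, +20%, +40% and +60%, gave mean estimates of:

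- B1/B2 only: 0.0508
- B1/B2 plus sequence as a fixed effect: 0.0508
- Period (four levels): 0.0401

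A sequence term does nothing here. A period term removes the bias. The fixed-effect design has rank 4 with or without B1/B2 added to period, so the B1/B2 contrast is already contained in period.

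**The case against.** The strongest reply is that the simpler model may be just as accurate in practice. No period trend is documented, and the design works against one: single doses, at least 7 days of washout, fasting, a standard diet while resident, restricted medication and one centre. With 23 df the 90% CI already runs from 0.65 to 1.76 times the estimate, so a bias of a few percent is small beside the sampling error. In root-mean-square error the two models break even at log steps of about 0.067 for AUC (exp(0.134) = 1.14, a 14% rise from Period 1 to Period 3) and about 0.12 for Cmax (exp(0.24) = 1.27). Below those drifts the planned model does equally well or slightly better. All of this stands. It limits the importance of the point but does not remove it, because the stated 90% CI relies on a residual free of period differences and the plan does not ensure that.

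A reader might infer more than the protocol supports:

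- *That any period effect biases the estimate.* It does not: a shift confined to Period 4 is fully absorbed by B1/B2.
- *That the estimate will be used to size later studies.* The protocol does not say so. The rationale in section 1.2 mentions future clinical pharmacology studies only in connection with the safety database.
- *That adding period would make the estimate comparable with the residual of the B versus A model.* It would not. That residual comes from different formulations and can contain volunteer-by-formulation variation, whereas this one comes from repeat doses of a single formulation.

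**Conclusion.** The point holds in a limited form. The planned model counts differences among Periods 1, 2 and 3 as within-volunteer variance. The bias can only be upward, and it is zero if those three periods do not differ. On assumed equal log steps of 0.05 to 0.20 per period with 24 volunteers, it is about 2% to 35% for AUC and 1% to 11% for Cmax. For AUC, 90% CI coverage falls to about 88% at a step of 0.10 and 82% at 0.15. The upper end needs exposure to be 49% higher in Period 3 than in Period 1, which nothing in the protocol suggests. Modest drifts give single-digit inflation.

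Only a secondary variance estimate and its CI are affected. The B versus A comparison has its own period term and uses Periods 1 to 3 only, and the sample size in section 12.3 rests on data from an earlier study. The algebra is certain; the practical size is unknown. This is a cheap improvement worth making, not a flaw that threatens the study.

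**What to change.** In section 12.2.2, in the Treatment B model for both AUC and Cmax, replace the two-level B1/B2 factor by period with four levels, and keep volunteer within sequence as the random effect. Period 4 is B2, so nothing in the B1/B2 contrast is lost. The model then adjusts for period as the B versus A model already does.

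The cost is two residual degrees of freedom with 24 volunteers (23 to 21). The upper 90% CI factor for the variance, df divided by the 5% point of chi-square, moves from 23/13.09 = 1.76 to 21/11.59 = 1.81. If there is no period effect, root-mean-square error rises by a factor of sqrt(23/21) = 1.047, or about 4 to 5%. Design, sampling and sample size do not change.

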12.2.3 Subject characteristics

Continuous variables (eg, age and height) will be summarized using descriptive statistics (n, mean, SD, minimum, median, and maximum). Categorical variables (eg, sex and race) will be summarized in frequency tables (frequency and proportion) for all volunteers overall.

12.2.4 Safety and tolerability

All safety data (scheduled and unscheduled) will be presented in the data listings. Continuous variables (hematology, clinical chemistry, dECGs, and vital signs) will be summarized using descriptive statistics (n, mean, SD, minimum, median, and maximum) by treatment or scheduled time point, as appropriate. Categorical variables (eg, urinalysis, etc) will be summarized in frequency tables (frequency and proportion) by treatment group or scheduled time point, as appropriate. Where applicable, data will be summarized for the absolute value at each scheduled assessment, and for the corresponding change from baseline. Adverse events will be summarized in frequency tables (frequency and proportion) for each treatment. Graphical presentations may be used, as appropriate.

All AEs will be collected for each volunteer from Day -1 until the follow-up visit. Adverse events that occur before the first dose of IP will be listed only. On-treatment AEs (ie, those beginning after the first dose of IP) will be summarized by preferred term and system organ class using MedDRA vocabulary with volunteer counts and percentages and also by severity and casualty. Furthermore, listings of deaths (if any), SAEs, and AEs that lead to study discontinuation will be made. The number of volunteers who have any AEs, SAEs, AEs that lead to withdrawal, AEs of different intensity, and AEs judged causally related to IP by the Investigator will be summarized.

For clinical laboratory tests, listings of values for each volunteer will be presented with abnormal or out-of-range values flagged. Clinical laboratory data will be reported in Système International units in the CSR. Shifts in clinical laboratory data will be tabulated.

Results from the physical examinations, pECGs, echocardiograms, and eye examinations will be presented in listings only.

The dECG parameters will be summarized for the absolute value at each scheduled assessment, together with the corresponding changes from the predose value. For safety purposes the QT correction factor will be based on the Frederica's formula (QTcF). Categorical summaries of absolute QTcF values (greater than 450 ms, greater than 480 ms, and greater than 500 ms) and change-from-predose values in QTcF values (greater than 30 ms and greater than 60 ms) will be produced. Further, safety data will be judged regarding low/high values or significant changes from predose using the AstraZeneca extended reference limits. Safety variables should be presented in the units indicated by the AstraZeneca extended reference limits. Abnormalities found on physical examination will be listed.

A shift plot showing predose QTcF values on the horizontal axis and last postdose QTcF value on the vertical axis. All 4 treatments will be plotted separately. The diagonal will be indicated on the plot (ie, 45 degree line). A shift plot showing predose QTcF values on the horizontal axis and the QTcF value indicating the maximum increase from baseline on the vertical axis. All 4 treatments will be plotted separately. The diagonal will be indicated on the plot (ie, 45 degree line). Digital ECG parameter graphs of group mean effect per time point by treatment and mean change from baseline per time point by treatment will be produced for all ECG parameters.

Extra measurements (such as unscheduled or repeat assessments) will not be included in the descriptive statistics, but will be included in data listings. All AEs and clinical laboratory and vital sign outliers that occur following the first dose of IP will be included in the tabulations of AEs and outlier events, including episodes that occur at unscheduled evaluations or during the washout period between treatments.

12.3 Determination of sample size

AUC₍₀₋₁₂₎ and C_{max} data from Study D1532C00005 (Part A, Day 1 single dose and Day 8 steady state) have been used to provide estimates of within-volunteer variability. Based on the estimate of within-volunteer variability of 0.04, 24 evaluable volunteers (4 per sequence) will provide 95% power to show that the 90% CI for the ratio of the population geometric means, based on log-transformed data, is contained in the limits of 80.00% to 125.00% for AUC. Based on the estimate of within-volunteer variability of 0.13 and a sample size of 24 volunteers, the upper limit of the 80% CI of an observed increase in C_{max} of 25% would be 1.43, which is considered clinically acceptable. In order to ensure that 24 evaluable volunteers complete the study, 30 volunteers (5/sequence) will be recruited.

Revised Clinical Study Protocol
Drug Substance AZD6244
Study Code D1532C00066
Edition Number 1
Date

The number of volunteers who will agree to participate in the genetic research is unknown. It is therefore not possible to establish whether sufficient data will be collected to allow a formal statistical evaluation or whether only descriptive statistics will be generated.

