Utilizing data from the first 3 treatment periods only, the relative bioavailability between treatments will be assessed between test (Treatment B) and reference (Treatments A) treatments. Analyses will be performed using a linear mixed-effect analysis of variance model using the logarithm of AUC and C_{max} . Transformed back from the logarithmic scale, geometric least-squares means together with confidence intervals (2-sided 95%) for AUC and C_{max} will be estimated and presented. Also, ratios of geometric least-squares means together with confidence intervals (2-sided 90%) will be estimated and presented. Using a similar model as above, comparisons will be made for dose-normalized AUC and C_{max} between test (Treatment B) and reference (Treatments C) treatment. AUC and C_{max} will be dose-normalized prior to the ln-transformation.

Using Treatment B data only, estimates of between- and within-volunteer variability will be obtained by employing a linear mixed-effect analysis of variance model using the logarithm of AUC and C_{max} . Estimates for the between- and within-volunteer variability will be present together with the associated 90% confidence intervals.

TABLE OF CONTENTS	PAGE
TITLE PAGE.....	1
PROTOCOL SYNOPSIS	2
TABLE OF CONTENTS	6
LIST OF ABBREVIATIONS AND DEFINITION OF TERMS.....	10
1. INTRODUCTION	13
1.1 Background.....	13
1.1.1 Nonclinical experience with AZD6244	13
1.1.2 Clinical experience with AZD6244	13
1.2 Rationale for conducting this study	15
1.3 Benefit/risk and ethical assessment	15
1.3.1 Safety considerations	15
1.3.2 Adverse event profile	15
1.3.3 Safety monitoring.....	18
2. STUDY OBJECTIVES.....	18
2.1 Primary objective	18
2.2 Secondary objectives.....	18
2.3 Exploratory objectives	18
3. STUDY PLAN AND PROCEDURES	19
3.1 Overall study design and flow chart	19
3.2 Individual stopping criteria.....	25
3.3 Rationale for study design, doses, and control groups.....	26
4. SUBJECT SELECTION CRITERIA.....	27
4.1 Inclusion criteria	27
4.2 Exclusion criteria	27
5. STUDY CONDUCT	30
5.1 Restrictions during the study	30
5.2 Subject enrollment, randomization, and initiation of investigational product.....	32
5.3 Procedures for handling subjects incorrectly enrolled, randomized, or initiated on investigational product.....	33

5.4	Blinding and procedures for unblinding the study.....	33
5.4.1	Methods for ensuring blinding	33
5.4.2	Methods for unblinding the study	33
5.5	Treatments	33
5.5.1	Identity of investigational product(s).....	33

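### Section 12.3 justifies the Cmax precision with an 80% confidence limit (1.43), but the planned analysis reports a 2-sided 90% interval, whose upper limit would be 1.49

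*Protocol*

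**What the plan says.** - **Primary parameters.** Section 12.2.2 states: "Primary PK parameters are AUC and" Cmax of AZD6244.
- **Reported interval.** For the treatment ratios, Section 12.2.2 says "ratios of geometric least squares means together with CI (2-sided 90%) will be estimated and presented". The synopsis has the same rule: "ratios of geometric least-squares means together with confidence intervals (2-sided 90%) will be estimated and presented". The 95% level that also appears there belongs to the geometric least-squares means of each treatment, not to the ratios.
- **Sample size, AUC.** Section 12.3 says that "24 evaluable volunteers (4 per sequence) will provide 95% power" for the 90% interval to lie within 80.00% to 125.00%. That sentence is limited to AUC and uses a within-volunteer variability of 0.04.
- **Sample size, Cmax.** The next sentence of Section 12.3 changes both the criterion and the level. It begins "Based on the estimate of within-volunteer variability of 0.13 and a sample size of 24 volunteers", then gives "the upper limit of the 80% CI of an observed increase in" Cmax "of 25% would be 1.43, which is considered clinically acceptable".

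No reason is given for moving from 90% to 80% within one paragraph, and no analysis section plans an 80% interval.

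**The concern.** The Cmax sentence is the only place where the protocol says what precision the trial will have for this primary parameter, and the only place where it judges that precision adequate. Both statements rest on an 80% interval. In the very case that Section 12.3 describes (24 volunteers, observed ratio 1.25), the report would show a wider interval with a higher upper limit. The sponsor's acceptability judgement would not have been made about that limit.

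What is at stake is modest but real. If the judgement on the reported limit is left open, it will be made after the results are known.

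**Working it through.** **Inputs**

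- Within-volunteer variability for Cmax: 0.13 (Section 12.3). The section does not name the scale. It is read here as a log-scale variance and tested below.
- Evaluable volunteers: 24 (Section 12.3).
- Observed ratio: 1.25 (Section 12.3, a 25% increase).
- Level in the justification: 80% (Section 12.3). Level in the analysis: 2-sided 90% (Section 12.2.2 and synopsis).
- Residual degrees of freedom: the model uses the first three periods, so 24 completers give 72 observations, and 72 − 24 (volunteers) − 2 (periods) − 2 (treatments) = 44. A two-treatment, two-period count, 48 − 24 − 1 − 1 = 22, and the normal quantile serve as brackets.

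**Formula**

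Standard error of the log ratio = √(2 × 0.13 / 24) = √0.010833 = 0.1041.

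Limits = 1.25 × exp(±q × 0.1041), where q is the 0.90 quantile for an 80% interval and the 0.95 quantile for a 90% interval.

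**Step 1: reproduce the plan's figure (80%)**

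- t, 44 df: q = 1.301; 1.25 × exp(0.1354) = 1.431
- t, 22 df: 1.434
- Normal: 1.428

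All round to 1.43, so the stated figure reproduces.

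**Step 2: test the reading of 0.13**

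| Reading of 0.13 | 80% upper | 90% upper | 95% upper |
|---|---|---|---|
| Within-volunteer variance | 1.43 | 1.49 | 1.54 |
| Standard deviation or CV | 1.31 | 1.33 | 1.35 |
| Variance of the within-volunteer difference | 1.38 | 1.41 | 1.45 |

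(All at 44 df.) Only the variance reading at 80% gives 1.43. The AUC sentence points the same way: taking 0.04 as a variance, with 24 volunteers and a true ratio of 1.00, the two one-sided tests have power 96.4% (22 df) to 96.9% (44 df), close to the stated 95%. Taking 0.04 as a standard deviation would give power of essentially 100%.

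**Step 3: same inputs at the level that will be reported (2-sided 90%)**

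- t, 44 df: q = 1.680; 1.25 × exp(0.1749) = 1.489; lower limit 1.25 × exp(−0.1749) = 1.049
- t, 22 df: upper limit 1.495 (1.4946 before rounding)
- Normal: upper limit 1.483

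The reported interval would be 1.05 to 1.49, with the upper limit between 1.48 and 1.49 to two decimals. The 80% interval on 44 df is 1.09 to 1.43.

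**The case against.** The strongest reply is that nothing in Section 12.3 is false. The level is openly stated as 80%, and 1.43 is right at that level. The sentence illustrates precision at one hypothetical observed value. No endpoint, model, decision rule or sample size depends on it, and Section 12.2.2 fixes the reported interval whatever Section 12.3 says. All of this stands, and it is why the point is a consistency correction and not a serious fault.

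It can also be said that the upper end of a 2-sided 80% interval is a one-sided 90% upper bound, a coherent way to express a worst-case increase. That may be where the figure came from. The protocol does not say so, however, and both analysis passages specify a 2-sided interval, so this does not reconcile them.

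A reader might draw stronger conclusions that the protocol does not support:

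- **That 80% is a slip for 90%.** It is not, because 1.43 does not come out at 90%. Changing the level alone would make the sentence wrong.
- **That the trial is too small for Cmax.** With variance 0.13 and a true ratio of 1.00, the chance that the Cmax 90% interval falls inside 80% to 125% is about 34% (22 df) to 36% (44 df). But the protocol sets that criterion for AUC only; Cmax is to be estimated and presented. A low probability of meeting a criterion that was never set is not a deficiency.
- **That the 95% power is claimed for Cmax too.** The power sentence is expressly limited to AUC.
- **That leaving out a decrease is an error.** The primary objective is only to compare the pharmacokinetics, and the same standard error gives the lower side directly. Showing it would be a matter of preference.

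**Conclusion.** The mismatch is real. The precision statement for a primary parameter is made at 80%, the analysis reports 2-sided 90%, and the sponsor's judgement of acceptability is tied to the former. The upper limit moves from 1.43 to 1.49, so the reported interval is less favourable than the stated one by about 0.06 on the ratio scale.

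This rests on reading 0.13 as a within-volunteer log-scale variance (inferred, but well supported), on 24 completers, and on an observed ratio of exactly 1.25. The choice of quantile moves the 90% upper limit only between 1.48 and 1.49.

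It does not follow that 1.49 is unacceptable. Section 12.3 says that 1.43 is acceptable; it does not say that 1.43 is the most that would be. The open question is whether the judgement also holds at the reported limit. The correction is worth making but is not critical to the trial.

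**What to change.** Choose one of two changes:

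1. **Restate Section 12.3 at the reported level.** Suggested wording: assuming a within-volunteer variance of 0.13 on the log scale and 24 evaluable volunteers, an observed Cmax ratio of 1.25 would have a 2-sided 90% confidence interval of 1.05 to 1.49. The sponsor then states, before results are seen, whether that upper limit is still clinically acceptable.
2. **Keep 80%.** Give the reason for that level in Section 12.3, and add the 80% interval for the Cmax ratio to Section 12.2.2 so that the justified figure is also reported.

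In either case, say that 0.13 is a variance on the log scale.

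The cost is a few sentences. Under the first option, the stated Cmax precision also becomes slightly less favourable. The sample size and conduct do not change, and neither does the primary analysis; the second option only adds one reported interval.
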